7.3 Methods of Imaging

Imaging should be acquired as outlined below and in Section 1.2 (Schedule of Events).

Contrast-enhanced CT of the chest; contrast-enhanced CT or MRI of the abdomen and pelvis; and all known sites of resected disease should be performed for tumor assessments. Images should be acquired with slice thickness of ≤ 5 mm with no intervening gap (contiguous). Every attempt should be made to image each patient using an identical acquisition protocol on the same scanner for all imaging time points. Tumor measurements should be made by the same Investigator or radiologist for each assessment whenever possible.

Should a patient have contraindication for CT intravenous contrast, a non-contrast CT of the chest and a contrast-enhanced MRI of the abdomen, pelvis, and all known sites of resected disease should be obtained.

Should a patient have contraindication for both MRI and CT intravenous contrasts, a non-contrast CT of the chest and a non-contrast MRI of the abdomen, pelvis, and all known sites of resected disease should be obtained.

Should a patient have contraindication for MRI (e.g., incompatible pacemaker) in addition to contraindication to CT intravenous contrast, a non-contrast CT of the chest, abdomen, pelvis, and all known sites of resected disease is acceptable after discussion and agreement with the Medical Monitor.

PET alone will not be considered for the disease assessment. Complementary CT and/or MRI and/or biopsy must be performed in such cases. Use of CT component of a PET-CT scanner: If a site can document that the CT performed as part of a PET-CT is of identical diagnostic quality to a diagnostic CT, then the CT portion of the PET-CT can be used to determine recurrence.

Brain imaging for patients with baseline history of treated brain lesions: Brain MRI required at baseline (without and with contrast; head CT with contrast allowed on study if patient develops contraindication for MRI). Brain imaging for patients without baseline history of brain metastases: Brain MRI (without and with contrast; head CT with contrast allowed if MRI contraindicated).

Ultrasound of sentinel-node basin as surveillance imaging is required.

Histological or cytological evidence of recurrence should be attempted in all cases except for brain metastases when safe and clinically feasible.

For clinically detected new lesions:

- Superficial cutaneous lesions: the recurrence of melanoma must be confirmed by cytology/histology.
- Deep subcutaneous lesions and lymph node lesions should be documented by ultrasound and histological/cytological evidence should be attempted. In absence of pathology report, lesion recurrence will be documented with a CT scan/MRI.
- Tumor markers or auto-antibodies alone cannot be used to assess recurrence.

7.4 Patient-Reported Outcomes

Health-related quality of life (HRQoL) will be assessed at the time points stipulated in the Schedule of Events (Section 1.2) by EORTC QLQ-C30 and EQ-5D-5L in patients who are ≥ 18 years of age at the time of informed consent. The EORTC QLQ-C30 and EQ-5D-5L should be assessed before any other study-related procedures are performed, with the EORTC QLQ-C30 assessed before the EQ-5D-5L. Paper forms should be used when patients are in the clinic and phone script should be used when patients are in follow-up.

If the subject withdraws from the study prematurely, all attempts should be made to obtain a final quality of life questionnaire prior to subject discontinuation. Reasons for missing subject reported outcomes questionnaires should also be documented so that the appropriate imputation method can be employed to correct for missing data in the analysis.

The questionnaire will be completed by the subjects before any clinical assessments are performed and treatments administered at any given visit. If subjects refuse to complete all or any part of a questionnaire, this will be documented. Questionnaires should be completed in the language most familiar to each subject, and subjects should be given adequate time and space to complete the questionnaire.

7.4.1 EORTC QLQ-C30

The EORTC QLQ-C30 will be used as a measure of HRQoL. The EORTC QLQ-C30 is composed of both multi-item scales and single item measures. These include five functional scales (physical, role, emotional, cognitive and social), three symptom scales (fatigue, nausea/vomiting, and pain), a global health status/HRQoL scale, and six single items (dyspnea, insomnia, appetite loss, constipation, diarrhea, and financial difficulties). Each of the multi-item scales includes a different set of items – no item occurs in more than one scale.

The EORTC QLQ-C30 employs a week recall period for all items and a 4-point scale for the functional and symptom scales/items with response categories of “Not at all”, “A little”, “Quite a bit” and “Very much”. The two items assessing global health status/HRQoL utilize a 7-point scale ranging from 1 (“Very Poor”) to 7 (“Excellent”) (Aronson, 1993).

For the purpose of this study, the GH/QoL and physical functioning subscales were selected as secondary endpoints. These subscales were selected as most commonly used indicators of HRQoL across cancer indications. [REDACTED]

7.4.2 EQ-5D-5L

The EQ-5D-5L is a standardized measure of health status developed by the EuroQol Group in order to provide a simple, generic measure of health for clinical and economic appraisal (Herdman, 2011; EuroQol, 1990; Aronson, 1993). The EQ-5D-5L has 2 components: a descriptive system and a visual analogue scale. The EQ-5D-5L descriptive system comprises 5 dimensions: mobility, self-care, usual activities, pain/discomfort, and anxiety/depression. Each dimension has 5 levels including “no,” “slight,” “moderate,” “severe,” and “extreme” or “unable to.” A dimension for which there are no problems is said to be at level 1, while a dimension for which there are extreme problems is said to be at level 5. Accordingly, the vectors 11111 and 55555 represent the best health state and the worst health state, respectively, described by the EQ-5D-5L. Altogether, the instrument describes $5^5 = 3,125$ health states. Empirically derived weights can be applied to an individual’s responses to the EQ-5D-5L descriptive system to generate a utility index measuring the value to society of his or her current health. In addition,

the EQ-5D-5L visual analogue scale allows respondents to rate their own current health on a 101-point scale ranging from “best imaginable” to “worst imaginable” health. Thresholds for meaningful change for the EQ-5D-5L utility index and visual analogue scale in cancer patients have not been defined. The EQ-5D-5L is available in more than 130 languages.

A standardized script will be used to facilitate telephone administration of the EQ-5D-5L during Survival Follow-up Visits.

8.0 ASSESSMENT OF SAFETY

8.1 AE Definition and Assessment

An AE is defined as any untoward medical occurrence in a clinical investigation patient administered a pharmaceutical product, at any dose, not necessarily related to the treatment.

An AE can therefore be any unfavorable and unintended sign, symptom, or disease temporally associated with the use of a medicinal product, whether or not considered related to the medicinal product. An AE can also arise from any use of the drug and from any route of administration, formulation, dose, or overdose. This definition includes intercurrent illnesses or injuries, and exacerbation of pre-existing conditions. Clinical laboratory, vital sign, or physical examination abnormalities will only be reported as AEs if they are deemed clinically significant by the Investigator (e.g., associated with signs and symptoms, require treatment, or require follow-up). The Investigator should attempt to establish a diagnosis of the event based on signs, symptoms, and/or other clinical information. In such cases, the diagnosis will be documented as the AE and/or SAE and not the individual signs/symptoms.

An AE does not include:

- A medical or surgical procedure (e.g., surgery, endoscopy, tooth extraction, or transfusion); an AE is the underlying condition that leads to the procedure.
- Pre-existing diseases or conditions present or detected before start of study drug(s) administration that do not worsen or increase in severity or frequency after the administration of study drug(s).
- Situations where an untoward medical occurrence has not occurred (e.g., hospitalization for elective surgery for a condition that has not worsened on study, social and/or convenience admissions to grant families a respite in caring for a patient).
- Overdose of either study drug(s) or concomitant medication without any signs or symptoms.

8.2 Monitoring AEs

All AEs will be assessed by the Investigator and recorded, including but not limited to, the following: the event term, the date of onset and resolution, seriousness, severity, relationship to study drug(s), outcome, treatment of the event, and action taken with the study drug(s). AEs will be reported starting immediately after the patient has been administered the first dose of study drug(s) until 100 (\pm 7) days following the last dose of study treatment(s) (Safety Follow-up Visit 2). For treatment-related SAEs, additional reporting requirements also apply (see Section 8.7).

An event occurring after the patient has provided informed consent, but before the first dose of study treatment or confirmed screen failure, will be collected as medical history unless the event is either new and attributed to protocol-mandated procedures by the Investigator or there is a significant change in the rate of occurrence or an increase in the severity of the pre-existing

condition which is judged to be clinically important and attributed to the protocol-mandated procedures by the Investigator. Under the latter 2 circumstances, the event will be considered an AE and will be captured as such.

- Example 1: Thrombophlebitis associated with a blood draw for assessments required prior to dosing per protocol is an event that is related to protocol-mandated procedures. In this scenario, the event of “thrombophlebitis” will be captured as an AE, and it will be documented as being “unrelated” to study drug(s), as applicable.
- Example 2: An ankle sprain following an unexpected fall from a flight of stairs while at home, after the patient has provided informed consent, but before the first dose of study drug(s), is clearly unrelated to any protocol-mandated procedures and would therefore be captured as medical history.

8.3 Grading of AEs

The severity of an event and the seriousness are not to be considered synonymous. The severity is grading the intensity of an event. The seriousness of event is based on the patient/event outcome or action criteria. All AEs will be assessed for severity using the National Cancer Institute Common Terminology Criteria for Adverse Events (NCI-CTCAE) version 5.0 guidelines. If a particular AE is not listed in the NCI-CTCAE, the following criteria will be used:

- Grade 1 = Mild (event results in mild or transient discomfort, not requiring or needing only minimal intervention or treatment; does not limit or interfere with daily activities [e.g., insomnia, mild headache]).
- Grade 2 = Moderate (event is sufficiently discomforting so as to limit or interfere with daily activities; may require interventional treatment [e.g., fever requiring antipyretic medication]).
- Grade 3 = Severe (event results in significant symptoms that prevent normal daily activities; may require hospitalization or invasive intervention).
- Grade 4 = Life-threatening or disabling.
- Grade 5 = Death.

Severity for all AEs will be recorded according to the highest severity grade a patient experiences for the duration of that AE.

8.4 Causality Relationship of AEs

The relationship of each AE to each study drug (bempegaldesleukin and/or nivolumab) as applicable will be evaluated by the Investigator using the following definitions:

- Not related: An AE that does not follow a reasonable temporal sequence from administration of study drug(s), and/or that can be reasonably explained by other factors such as the patient’s pre-existing medical condition, underlying disease, concurrent illness, or concomitant medications/therapies.

- Related: There is a reasonable possibility that the AE is caused by the study drug(s). A plausible temporal sequence exists between the time of administration of the study drug(s) and the development of the AE. The AE cannot be reasonably explained by the known characteristics of the patient's clinical state or other concomitant therapies or interventions administered to the patient.

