5.10 Dosage Modification

If bempegaldesleukin or nivolumab meet the criteria for dose delay, then administration of both drugs must be delayed until the criteria to resume are met (Section 5.10.3).

Note: Imaging assessments for all patients should continue as per protocol even if dosing is delayed.

Patients who require a dose delay of nivolumab or bempegaldesleukin should be re-evaluated weekly or more frequently if clinically indicated and should resume treatment with combination of bempegaldesleukin and nivolumab when retreatment criteria are met (Section 5.10.1). Immuno-oncology agents are associated with AEs that can differ in severity and duration from AEs caused by other therapeutic classes. Bempegaldesleukin and nivolumab are considered immuno-oncology agents in this protocol. Early recognition and management of AEs associated with immuno-oncology agents may mitigate severe toxicity.

Discontinuation criteria for bempegaldesleukin and nivolumab are provided in Section 5.12.

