5.10.1 Dose Delay and Reduction Criteria

5.10.1.1 Arm A: Bempegaldesleukin Dose Delay and Reduction Criteria

Dose delays and one dose reduction are permitted for bempegaldesleukin. Bempegaldesleukin may be delayed or reduced to 0.003 mg/kg based on observed treatment-related toxicities. Medical Monitor consultation is required for dose reduction. If the bempegaldesleukin dose is reduced to 0.003 mg/kg, the dose level should remain at this level throughout the remainder of the study and cannot be re-escalated. If bempegaldesleukin meets the criteria for dose delay, then administration of both drugs (for patients on Arm A) must be delayed until the criteria to resume are met.

Bempegaldesleukin administration should be delayed or reduced for the following reasons:

- For persistent Grade 2 treatment-related AE
 - Definition of persistent Grade 2 treatment-related AE: A Grade 2 AE lasting at least 3 weeks and ongoing at the time of subsequent dosing that is attributed as either “possibly related” or “related” to bempegaldesleukin
 - Dose delay or dose reduction:
 - For the 1st or 2nd occurrence of the same persistent Grade 2 treatment-related AE, bempegaldesleukin administration should be delayed until the treatment-related AE resolves to Grade 1 or baseline, and the treatment-related AE should be treated symptomatically.
 - After the 1st occurrence, bempegaldesleukin may be continued at 0.006 mg/kg.
 - After the 2nd occurrence, bempegaldesleukin should be dose-reduced from 0.006 mg/kg to 0.003 mg/kg.
 - Treatment discontinuation: After the 3rd occurrence, discontinuation of bempegaldesleukin may be considered in consultation with the Medical Monitor.
 - Special cases
 - Persistent Grade 2 treatment-related AEs of constitutional and flu-like symptoms (fever, chill, myalgia/arthralgia) except fatigue and asthenia: please follow management guideline above, plus prophylactic medication (e.g., nonsteroidal anti-inflammatory drugs, antipyretic, antihistamine) should be considered. Persistent Grade 2 treatment-related AEs of fatigue and asthenia do not require dose delay or reduction.
 - For Grade 2 treatment-related AEs listed below, please see relevant protocol section for specific management guidelines.
 - Grade 2 treatment-related AEs except fatigue and asthenia (not applicable)
 - Creatinine increase (see Grade \geq 2 creatinine increase below)

- AST/ALT elevations (Section 5.10.2)
 - Elevated hepatic transaminases (Section 5.11.1)

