 - Adrenal insufficiency and hypophysitis (Section 5.11.2)
 - Eosinophilia (Section 5.11.3)
 - Immune-mediated AE (Section 5.11.4)
 - Infusion-related reactions (Section 5.11.5)
 - Immediate infusion-related reactions, flu-like symptoms, and hypersensitivity events (Section 5.13.1)
- Grade ≥ 2 creatinine increase
 - For patients who must delay study treatment due to Grade ≥ 2 creatinine increase due to a non-inflammatory cause, delay retreatment with study drug for approximately 3 to 5 days. After the dosing delay, the patient may resume study drug when serum creatinine has returned to Grade ≤ 1 , as assessed within 24 hours prior to redosing (or as soon as locally feasible). Refer to renal AE management algorithm in the current nivolumab Investigator's Brochure for further guidance.
 - Grade ≥ 3 AE at least possibly related to bempegaldesleukin: bempegaldesleukin must be delayed until resolution to Grade 1 or baseline (unless otherwise requiring permanent discontinuation, per Section 5.12.1), with the following exceptions:
 - Grade ≥ 3 lymphopenia
 - Grade ≥ 3 asymptomatic amylase or lipase elevation

Bempegaldesleukin dosing may resume at the same bempegaldesleukin dose or at a lower bempegaldesleukin dose level when toxicity resolves to Grade 1 or returns to baseline, except for instances where the potential recurrence of the event poses an undue risk for the patient (see Section 5.12.1 for permanent discontinuation criteria).

Note: For Grade ≥ 3 AEs that cause dose delay, if biopsy of AE-affected organ is conducted, tissue specimen for biomarker analysis is highly recommended (see Section 5.8.1). Five to 10 slides are recommended, with a minimum of 5 slides.

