5.10.3 Criteria to Resume Bempegaldesleukin and/or Nivolumab

Patients may resume treatment when the treatment-related AE(s) resolve(s) to Grade ≤ 1 or baseline, with the following exceptions:

- Patients may resume treatment in the presence of Grade 2 fatigue.
- Patients who have not experienced a Grade 3 treatment-related skin AE may resume treatment in the presence of Grade 2 skin toxicity.
- Patients with baseline Grade 2 AST/ALT and/or total bilirubin abnormalities may resume dosing when laboratory values return to baseline and management with corticosteroids, if needed, is complete.
- Treatment-related pulmonary toxicity, diarrhea, or colitis must have resolved to baseline before treatment is resumed. Patients with persistent Grade 1 pneumonitis after completion of a steroid taper over at least 1 month may be eligible to resume study treatment if discussed and approved by Medical Monitor.
- Patients with treatment-related endocrinopathies adequately controlled with only physiologic hormone replacement may resume treatment after consultation with the Medical Monitor (or designee). Grade ≥ 3 adrenal insufficiency and/or Grade 4 hypophysitis require discontinuation regardless of control with hormone replacement (see Section 5.12.1 for permanent treatment discontinuation criteria). Hospitalization for diagnostic workup of adrenal insufficiency without severe symptoms should not require discontinuation.

- For patients who must delay study treatment due to Grade ≥ 2 creatinine increase due to a non-inflammatory cause (Section 5.10.1), delay retreatment with study drug for approximately 3 to 5 days. After the dosing delay, the patient may resume study drug when serum creatinine has returned to Grade ≤ 1 , as assessed within 24 hours prior to redosing (or as soon as locally feasible), except where permanent discontinuation of study drug is required (Section 5.12.1).

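### Protocol 8.4's two causality definitions conflict for an AE with both a reasonable drug cause and a reasonable alternative cause, and 5.10.1.1 acts on a *possibly related* level that 8.4 does not define

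*Protocol*

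**What the plan says.** Protocol 8.4 asks the investigator to judge each AE against each study drug and offers two categories.

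- **Related** has three sentences. The first is "There is a reasonable possibility that the AE is caused by the study drug(s". The second asks for plausible timing. The third begins "The AE cannot be reasonably explained by the known characteristics of" the patient's clinical state and extends to other therapies.
- **Not related** is met by a lack of reasonable timing "and/or that can be reasonably explained by other factors such as" the patient's medical condition, underlying disease, concurrent illness or other treatments.

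Section 5.10.1.1 uses a different scale. A persistent Grade 2 treatment-related AE is one "that is attributed as either “possibly related” or “related” to bempegaldesleukin". For Grade 3 or higher the trigger is an "AE at least possibly related to bempegaldesleukin: bempegaldesleukin must be delayed until resolution to Grade 1 or baseline", with the carve-out "unless otherwise requiring permanent discontinuation, per Section 5.12.1".

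The 8.4 label then feeds other rules:

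- Section 8.7 requires SAEs starting beyond 100 (±7) days after the last dose to be reported only if assessed as related.
- Section 8.8 continues follow-up past Safety Follow-up Visit 2 only for treatment-related SAEs.
- SAP 7.1 tabulates drug-related TEAEs and counts a missing relationship as related.

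**The concern.** Events with more than one plausible cause are the ones for which a causality scale most needs a clear rule. Take atrial fibrillation in a patient with a cardiac history. Protocol 2.1.3.2.4 lists it at 0.6% among treatment-related SAEs in the pooled doublet data. Exclusion criterion 19 removes only cardiovascular disease that was unstable or deteriorating in the 12 months before Screening, so patients with a plausible cardiac alternative can enroll. The 0.6% illustrates the kind of event; it does not estimate how many have two plausible causes.

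If 8.4 pushes such an event to Not related, late safety information is lost. If it leaves the answer open, two investigators can follow the protocol and give opposite answers for the same event. In either case the drug-related table depends on how 8.4 was read. The undefined *possibly related* level adds a second uncertainty: the protocol uses *treatment-related* without one fixed meaning.

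**Working it through.** No sample size, power or event count is involved. The check reads 8.4 as a decision rule and traces the label through the sections that use it.

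**Step 1. Apply 8.4 to AEs with plausible timing.**

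| Reasonable causes | Related, first sentence | Related, last sentence | Not related, second limb | Result |
|---|---|---|---|---|
| Drug only | met | met | not met | Related |
| Alternative only | not met | not met | met | Not related |
| Both | met | not met | met | conflict |

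**Step 2. Resolve the third row.** Three readings are possible.

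- All three sentences of Related are required: Not related only. This is the most literal reading.
- The first sentence is enough: the AE meets both definitions.
- *Explained* means fully accounted for by the alternative: Related. Section 8.4 does not say this.

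**Step 3. Trace a Not related record.**

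- *8.8.* Follow-up of an unrelated SAE ends at resolution or the last Safety Follow-up Visit. Follow-up of a related SAE goes on until the event resolves, stabilizes or returns to baseline, no more information can be had, or the patient dies or is lost. The label therefore matters only for an SAE unresolved and not yet stabilized at Visit 2.
- *8.7.* A non-AESI SAE with onset beyond 100 (±7) days need not be reported to the sponsor.
- *SAP 7.1.* The AE leaves the drug-related TEAE table, 1 of 7 summaries. A blank relationship would have kept it in.

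That is 1 + 1 + 1 = 3 rules or outputs.

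**Step 4. Check what *treatment-related* means elsewhere.** In the persistent Grade 2 rule of 5.10.1.1 it includes *possibly related*. Section 5.10.3 seems to follow that use, since patients held under 5.10.1.1 come back under it: "Patients may resume treatment when the treatment-related AE(s) resolve(s". In 8.2 it points to 8.7, where it means the 8.4 answer. Sections 5.12.1 and 5.10.1.2 do not say which applies.

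- Section 5.12.1: 5 of 9 criteria use the term, or 4 of 8 if the liver-function bullet is nested under the one above it.
- Section 5.10.1.2: 4 of 5 criteria use it.
- Total with unclear wording: 5 + 4 = 9, or 4 + 4 = 8.

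For 5.10.1.2 this matters only where 5.10.1.1 has not already stopped dosing, because under 5.10, if either drug meets its delay criteria, "then administration of both drugs must be delayed until the criteria to resume are met". These are counts of rules, not of patients or events.

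**Step 5. List what does not depend on the 8.4 label.**

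- The 5.10.1.1 hold, whose trigger is wider than Related.
- SAE reporting within 100 (±7) days, which is regardless of causality (8.7).
- AESI reporting (8.10).
- IMAEs, counted regardless of causality (SAP 7.2).
- The all-causality TEAE, serious, Grade 3 or above, discontinuation and death summaries (SAP 7.1).
- The investigator-judgment criteria in 5.10.1.2 and 5.12.1.

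**The case against.** The strongest reply is that 8.4 is not as strict as its last sentence suggests. The three sentences of Related are not joined by *and*, and the first sets the familiar standard. An investigator could rely on it alone, or read the alternative-explanation clause as covering only alternatives that fully account for the event. This stands in part. A reader might infer that 8.4 always records a dual-cause event as Not related; the text does not support that certainty. But the reply replaces a wrong answer with an indeterminate one, because the second limb of Not related still applies on the text as written.

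Other limits also stand.

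- Section 8.8 follow-up of related SAEs ends at stabilization, so a stable arrhythmia would be dropped at Visit 2 under either label.
- Table 4 marks AE and SAE assessment at survival contacts, but refers to 8.5 and 8.8 for how long events are followed.
- Section 12.1 provides for notifying the IRB or IEC of any SAE under local requirements. That is a partial backstop and does not create a report to the sponsor under 8.7.
- *Possibly related* widens the 5.10.1.1 trigger, so a reader who infers that dosing protection is lost there would be mistaken.
- SAEs starting beyond 100 days fall outside even the extended treatment-emergent period in SAP 6.6, so the 8.7 gap changes no TEAE table.
- The program ended on 14 April 2022, and the SAP plans only descriptive summaries by arm.

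**Conclusion.** The point holds as a conflict in wording with bounded safety consequences. Section 8.4 gives no consistent answer for an AE with both a reasonable drug cause and a reasonable alternative; the most literal answer is Not related. Section 5.10.1.1 uses a level that 8.4 does not have. When such an event is recorded as Not related, the three consequences in Step 3 of the working follow, and no other section fully restores what is lost.

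The number of events cannot be estimated, because the documents give no count of AEs with more than one plausible cause. The 8 or 9 unclear criteria in 5.12.1 and 5.10.1.2 show ambiguity only. They do not show that any patient was wrongly kept on treatment.

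A reader might also infer a bias between arms, since only Arm A has the wider hold. The documents do not support that: the same 8.4 definitions apply to both arms, no event counts are given, and the SAP drops all comparative analyses.

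Termination reduces the practical reach but does not remove the point. About 774 patients were enrolled (SAP 5.1), the drug-related TEAE table is still planned, and the late-onset duty in 8.7 has no stated end. The conclusion assumes that investigators applied 8.4 as printed, without other guidance that the documents do not show.

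**What to change.** - In 8.4, define Related as a reasonable possibility that the study drug caused or contributed to the AE.
- Delete the last sentence of Related and the matching alternative-explanation limb of Not related.
- In 5.10.1.1, replace *possibly related* with Related.
- State that *treatment-related* in 5.10 and 5.12 means Related under 8.4.

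The cost is protocol and eCRF-guideline wording. Somewhat more AEs will be classed as related, with a few more mandatory delays, stops and late SAE reports; the documents give no basis for a number. New wording does not reclassify events already recorded, so the SAP 7.1 drug-related table should be read beside the all-causality tables.
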